5.2 Analysis Sets

The analysis will be performed on the total of vaccinated subjects included in the study. The analysis will be conducted using injected group (QIV-HD vs QIV-SD) for almost all analysis. For analysis(es) according to randomized group, a clear information will be available on the title of the output.

Sub-analysis sets will be considered when other factors are used (eg, age, sex).

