## 12.2 Analysis Sets

The analysis will be performed on the total of vaccinated subjects included in the study. The analysis will be conducted using injected group.

Sub-analyses sets will be considered when other factors are used (eg, age, sex).

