## 12.3 Handling of Missing Data and Outliers

### 12.3.1 Effectiveness

A subject lost to follow-up could be considered as rare. Therefore, denominators will be subjects in the injected group.

Hospitalizations are captured throughout the usual process of national registry, and that permit a minimization of missing occurrences compared to a classical clinical study.

In any case, no replacement of data will be done.

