With the decision of stopping the study after the first year, the endpoints correspond only for the season 2019-2020. In addition, no influenza epidemic period was defined for 2019-2020 season, as only low/moderate flu incidence was observed in Finland.

Focus on input data:

A Data Transfer Agreement (DTA) document is available as version 4.0, and describes all data available for the study. The 12 panels available are the following:

- Thl_enr, linked to enrollment and injection
- Thl_drop, that identified subject withdrawal
- Thl_dev, that identified deviations at subject level
- Thl_hilm, corresponding to hospitalizations from HILMO registry
- Thl_er, corresponding to emergency room visits from HILMO registry
- Thl_avoh, corresponding to primary care visits to the physician from AVOHILMO registry
- Thl_hvac, corresponding to previous vaccinations (flu and pneumonia) from AVOHILMO registry
- Thl_lab, corresponding to positive flu and invasive bacterial detection from NIDR registry
- Thl_chro, corresponding to aggregated data for chronic diseases (comorbidity) from Social Insurance Institution (KELA) reimbursement registry
- Thl_cara, corresponding to aggregated data for care allowance due to disability from Social Insurance Institution (KELA) reimbursement registry
- Thl_med, corresponding to aggregated data for antimicrobial medications from Social Insurance Institution (KELA) reimbursement and prescription registries
- eSAE, corresponding to SAE entered by THL in SP eCRF database (death, related SAE, and AESI), and later available in SP PV database with MedDRA coding

In addition, 3 dictionaries are available for statistical analysis:

- ICD-10 codes: It corresponds to ICD-10 codes used at Finland level. Some adaptations are also applied (eg, code such as '###*' are simplified with '###').
- ICPC-2 codes: It corresponds to ICPC-2 codes used at Finland level.
 - One file contains all codes (even not linked to selected I/J ICD-10 codes).
 - One file with only codes linked to primary objectives, and with correspondences to the ICD-10 codes.

- MedDRA: eSAE panel already contains the MedDRA codes/labels. Therefore, no external dictionary is used.

Complementary to the files above, we also have two randomization files: the randomization of the subjects based on randomization order, and the randomization of the product (dose number).

We also have a file corresponding to the 41 HS (name, link with HCC) involved in the study.

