5.1.1.2 Statistical Methods

Primary endpoint will be derived using database extracted from the Finnish national registers.

In case of more than one occurrence for the same subject, only the first occurrence will be considered in the estimation of rVE.

The two-sided 95% CIs for rVE will be calculated by an exact method assuming a binomial distribution of the number of cases in QIV-HD group conditional on the total number of cases in both groups:

Let $q = \frac{C_{QIV-HD}}{C_{QIV-HD} + C_{QIV-SD}}$, the proportion of cases belonging to QIV-HD group among the total number of cases. Given the total number of cases, C_{QIV-HD} has a binomial distribution ($q, C_{QIV-HD} + C_{QIV-SD}$). Thus, a CI for q may be constructed using the exact Clopper-Pearson method for binomial proportions.

As $\frac{q}{1-q} = \frac{C_{QIV-HD}}{C_{QIV-SD}}$, the rVE estimate given above may be restated as follows:

$rVE = \left(1 - \frac{c_{QIV-HD}/N_{QIV-HD}}{c_{QIV-SD}/N_{QIV-SD}} \right) \times 100\% = \left(1 - \frac{N_{QIV-SD}}{N_{QIV-HD}} \times \frac{q}{1-q} \right) \times 100\%$, which is a strictly decreasing function of q.

Finally, for the primary endpoint, a CI of the rVE may be constructed based on the CI of q.

For the primary endpoint, the superiority of the QIV-HD effectiveness over QIV-SD will be considered demonstrated if the lower bound of the two-sided 95% CI for the rVE is above 0%.

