5.1.2 Hypotheses and Statistical Methods for Secondary and Observational Objectives

5.1.2.1 Hypotheses

No hypotheses will be tested.

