5.3 Handling of Missing Data and Outliers

5.3.1 Effectiveness

A subject lost to follow-up are considered rare in the register follow-up. Therefore, denominators will be subjects in the injected group.

Hospitalizations are captured throughout the usual process of national registry, and that permits a minimization of missing occurrences compared to a classical clinical study.

For subject who withdraws their consent, the data are also partial.

End dates for SAE will be also censored if they occur 31AUG2020, even if they continue thereafter.

In any case, no replacement of data will be done.

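### The only confirmatory superiority test groups subjects by vaccine injected, and no randomised-group analysis of the primary endpoint is named although both randomisation files are held

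*SAP*

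**What the plan says.** Protocol 12.2 takes all vaccinated subjects and states: "The analysis will be conducted using injected group". Protocol 12.3.1 repeats the rule for effectiveness: "A subject lost to follow-up could be considered as rare. Therefore, denominators will be subjects in the injected group". The SAP follows. Section 5.2 says "The analysis will be conducted using injected group (QIV-HD vs QIV-SD) for almost all analysis", and section 5.3.1 again sets the effectiveness denominators to the injected group. The two documents agree.

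The primary endpoint has a formal success rule in SAP 5.1.1.2: "superiority of the QIV-HD effectiveness over QIV-SD will be considered demonstrated if the lower bound of the two-sided 95% CI" for rVE is above 0%. For the secondary and observational objectives, SAP 5.1.2.1 says "No hypotheses will be tested". The primary test is therefore the only confirmatory one.

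On randomised-group analyses, SAP 5.2 says only: "For analysis(es) according to randomized group, a clear information will be available on the title of the output". It does not say which endpoint, if any, will have one. The supplementary analyses listed in SAP 5.1.2.2 (by factor, without potential COVID-19 cases, by person-years, Kaplan-Meier) include none by randomised group. SAP 4 confirms that the subject randomisation file and the dose-number randomisation file are both available.

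**The concern.** Randomisation makes the groups comparable as they were allocated. Grouping by product received lets membership depend on what happened after allocation. If subjects who got the other product differ in risk from the rest, and the switches run mainly one way, the injected-group comparison is biased even when the vaccines are equivalent. The as-randomised comparison keeps its type I error in that situation.

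Switching is possible here because the nurse who injects is unblinded (protocol 5.1.2). The same nurse role takes consent, checks eligibility, randomises and vaccinates (protocol 5.1.4). SAP 5.6 reviews deviations, randomisation numbers and product numbers on blinded data only, and no table of randomised versus injected group by arm is named. As the plan stands, a reader of the report could not tell whether the choice of grouping mattered. A randomised-group analysis that is allowed but not named could also be run or dropped after results are known.

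**Working it through.** **Reproducing the plan's figure.** Given D cases in total and 1:1 allocation, QIV-HD cases follow Bin(D, q) with q = RR/(1+RR). Success requires at most c cases in QIV-HD, where c is the largest value with P(X ≤ c | 0.5) ≤ 0.025. For D = 2200, c = 1053. At rVE 13% (RR 0.87, q = 0.4652) power is 89.99%, matching the stated 90.0%. At rVE 10, 11, 12, 14 and 15% the results are 68.7, 77.3, 84.5, 94.0 and 96.6%, so every row of SAP Table 5.2 reproduces. The test itself is correctly specified; only the grouping is at issue.

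**Inputs for the size of the effect.** 33 093 vaccinated (SAP 3.1) and about 450 cases (SAP 5.5). Assuming an even split, N = 33 093/2 = 16 546.5 per arm and p = 450/33 093 = 1.36%. No mismatch count is given, so the switch share m and the relative risk k of switched subjects are assumptions.

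**Bias under the null.** A share m of the QIV-HD arm, at risk k·p, receives QIV-SD:

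- Cases changing group = m·N·k·p.
- As-injected rVE = 1 − [(1−mk)/(1−m)] / [(1+mk)/(1+m)].
- The test uses null share q0 = (1−m)/2, while the true share is (1−mk)/2. The critical value for 450 cases is 203, 202 and 201 for m = 0.1%, 0.5% and 1%.

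| m (subjects) | Cases moved, k=2 | rVE shift, k=2 | Error, k=2 | Error, k=1.5 | Error, k=1 |
|---|---|---|---|---|---|
| 0 | 0 | 0 | 2.13% | 2.13% | 2.13% |
| 0.1% (17) | 0.45 | +0.20 | 2.35% | 2.30% | 2.24% |
| 0.5% (83) | 2.25 | +0.99 | 2.80% | 2.48% | 2.19% |
| 1% (165) | 4.50 | +1.98 | 3.65% | 2.88% | 2.25% |

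A switch in the opposite direction gives −0.20, −1.00 and −2.02 points at k = 2. At k = 1 the shift is zero, and the small changes in error come from the discreteness of the exact test.

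**Where the nominal level is passed.** Stepping through 0 to 331 switches, the error stays above 2.5% only beyond 63 one-way switches (63/16 546.5 = 0.38% of an arm) at k = 2, or 133 (0.80%) at k = 1.5. Because the test moves in steps, it first crosses 2.5% at 27 and 36 switches and then falls back.

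**Scale for comparison.** With 225 of 450 cases per arm, the Clopper-Pearson interval for rVE is −20.8% to +17.2%. Success needs at most 203 cases in QIV-HD: 203 gives a lower bound of +0.6%, and 204 gives −0.2%.

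**Cost of grouping as randomised.** Assume 1% random cross-over in both arms and true RR 0.87. The arm rates, relative to QIV-SD, become 0.99×0.87+0.01 = 0.8713 and 0.99+0.01×0.87 = 0.9987, so rVE = 12.76%. Exact power falls from 89.99% to 88.79% with 2200 cases, and from 29.02% to 28.02% with 450.

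**The case against.** The strongest reply is that this is a pre-specified choice on which the protocol and SAP agree, and that the harm is hypothetical. Bias needs mismatches that are mostly one-way and related to risk, and none is reported. Safeguards exist: numbers are used in list order, the group is hidden until scratched and shown as a product code, and an unusable dose is replaced with the same product (protocol 6.5). Dose labels go on both the list and the consent form (protocol 5.1.4), and deviations have their own data panel (SAP 4). Part of the small rise in error is discreteness: at m = 0.1%, 0.11 of the 0.22-point rise is present even without risk selection. The SAP already concedes inadequate power (5.7), so a shift of up to 2 points would rarely change the reading. Changing the primary grouping after follow-up has ended also departs from the protocol. Finally, the randomisation number could carry transcription errors that create false mismatches.

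Much of this stands and limits the size of the point. It does not remove it. Agreement between the documents does not make the grouping the better one for a superiority test, and the safeguards reduce selective switching without excluding it. The superiority rule remains in force despite low power. Transcription error is speculative; at worst it dilutes the result, and mismatches can be checked against the returned randomisation lists, which carry the dose labels. The SAP calls itself a core body, so the absence of a named randomised-group output is established only for the text available.

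**Conclusion.** The concern holds. The sole confirmatory test is by vaccine injected, and no randomised-group analysis of the primary endpoint is committed to, although the data for one are held. The consequence is conditional and probably small. Across the assumed range (0.1% to 1% of one arm switching one way at 1.5 or 2 times average risk, even split, about 450 cases, no true effect), rVE moves by at most about 2 points. Where the switch favours QIV-HD, the one-sided error lies between about 2.3% and 3.6%, against 2.1% with no mismatches. With no mismatches, or with chance ones, there is no bias under the null. The change is worth making because it is cheap and removes the question, not because there is evidence that switching occurred.

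**What to change.** Before unblinding:

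- In SAP 5.2 and 5.3.1, name vaccinated subjects by randomised group as the analysis for the primary endpoint test, and keep the injected-group result as a named sensitivity analysis.
- In SAP 5.7, record the departure from protocol 12.2 and 12.3.1.
- Add one post-unblinding table of randomised versus injected group by arm, separate from the blinded review in SAP 5.6.

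Safety, the untested secondary and observational endpoints, and the aggregated KELA panels can stay by injected group.

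The cost is edits to three SAP sections, a second group variable from the files already held, one extra run of the primary endpoint and one table. No new data are needed. Restricting to vaccinated subjects omits only 33 096 − 33 093 = 3 of those who signed consent. The downside is slight dilution if mismatches are random: about 1 percentage point of power at an assumed 1% symmetric cross-over.

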5.3 Handling of Missing Data and Outliers

5.3.1 Effectiveness

A subject lost to follow-up are considered rare in the register follow-up. Therefore, denominators will be subjects in the injected group.

Hospitalizations are captured throughout the usual process of national registry, and that permits a minimization of missing occurrences compared to a classical clinical study.

For subject who withdraws their consent, the data are also partial.

End dates for SAE will be also censored if they occur 31AUG2020, even if they continue thereafter.

In any case, no replacement of data will be done.

5.3.2 Safety

No replacement will be done.

5.4 Interim / Preliminary Analysis

No interim / preliminary analyses are planned up to the analysis of the primary and secondary objectives.

The analysis is planned to be conducted in one final step taking into account the full 2019-2020 season. A possibility is still open to explore more data later, if necessary, based on the main analysis.

5.5 Determination of Sample Size and Power Calculation

The sample size needed for the assessment of the primary objective of the study was expected to be approximately 121 000 subjects and may be adjusted based on the blinded number of cases in order to maintain the likelihood of achieving approximately 2200 evaluable subjects with at least 1 cardiovascular and/or respiratory hospitalization.

The 2200 evaluable cases would provide approximately 90% power (by exact method) to conclude on the primary objective under the following assumptions:

- The true rVE of QIV-HD over QIV-SD is 13% against prevention of cardiovascular and respiratory hospitalization
- 0.025 one sided type I error
- A lower bound on the rVE above 0%
- An allocation ratio between groups of 1:1

Considering:

- Approximately 450 cases were collected during the first season of the study.
- The expected attack rate of first occurrence of primary endpoint is approximately 2%, in the next seasons in Finland

The study power using different rVE assumptions is presented in [Table 5.2](#).

Table 5.2: Different rVE assumptions and associated study power for the sample size of 121000

rVE (%)	Study Power (%)
10	68.7
11	77.3
12	84.5
13	90.0
14	94.0
15	96.6

5.6 Data Review for Statistical Purposes

No formal data review was performed. The data from registry are not modifiable by nature. Some post-hoc exploration (on blinded data) will be done such as the review of the deviations, the randomization number and product number on data from OCE, the presence of codes in the dictionaries.

5.7 Changes in the Conduct of the Trial or Planned Analyses

Approximately 121 000 subjects 65 years of age and older were to be enrolled over multiple influenza seasons in the phase IIIb/IV registry-based trial (QHD00012).

The study was initiated in 2019-2020 influenza season and more than 33 000 subjects were enrolled. The first subject was included in November 2019 and the last subject data was collected in August 2020.

However, the impact of the COVID-19 global pandemic created significant challenges to conducting this clinical study such as:

- Low incidence rates for influenza and high COVID-19 rates had an impact on our study plan
- Low incidence rates for influenza hindered data collection and endpoints

Therefore, the study was on pause ie, no enrollment for the two seasons 2020-2021 and 2021-2022.

In Q1 2022, Sanofi Pasteur took the decision to stop the study, as uncertainties on influenza circulation for the coming seasons still remained.

Therefore, the study finally consists of a unique season (season 2019-2020), without significant flu circulation. This will result in inadequate power for the primary endpoint analysis.

For the primary endpoints, 3 codes will not be considered as not referenced in ICD-10 Finland and/or in ICD-10 WHO version 2019. The codes are: I16, I75 and I76.

The Finnish registries HILMO and AVOHILMO collect ICD-10 with start date of the event. Nevertheless, some details are not available (eg, death status). Therefore, MACE criteria is not formerly possible. The analysis is adapted with ICD-10 codes linked to MACE as follows:

- Any I20-I25 + I63 (linked to MACE)
- Ischaemic heart diseases (I20-I25)
 - Myocardial infarction (I21-I23) [I21 (Acute myocardial infarction), I22 (Subsequent myocardial infarction), and I23 (Certain current complications following acute myocardial infarction)]
 - Unstable angina (I20 + I25) [I20 (Angina pectoris) and I25 (Chronic ischaemic heart disease)]
- Cerebral infarction (I63)

The death is managed throughout eSAE information, as reported by THL. No panel are specifically identified coming from Statistics Finland registry.

After discussion with KELA, it was decided to obtain only aggregated data for 3 panels due to complex data privacy processes. Thus, this prevents submission of individual data for these secondary and observational endpoints to authorities such as FDA or EMA.

No analysis is anticipated linked to Social Welfare registry identified in the Table 11.1 of the protocol. Of note: No specific links objectives/endpoints are mentioned for these data in the protocol.

Additionally, in safety endpoint, we have in the protocol: "Occurrence and nature (MedDRA PT or ICD-10 codes) of non-fatal SAEs by time to onset and seriousness criteria up to 6 months after vaccination". Nevertheless, information around hospitalizations (from HILMO) don't include the

fatality. The hospitalization analysis (all SAE) will be conducted without considering fatality (non-fatal or fatal). Secondly, the seriousness analysis is based only on eSAE, as not available in all hospitalizations via HILMO registry.

Of note:

- Due to the context of the study no Adjudication Review Committee (ARC) was put in place. It was a possibility identified in the protocol to review primary outcomes.
- During the 2019-2020, no anti-influenza medications were observed in the study cohort. Therefore, only antibacterial data are present in thl_med.
- Regarding "Previous vaccinations during the last 5 years (administered product and date of vaccination)" as described in Section 5.2.6 of the protocol, data collected were restricted to flu and pneumonia vaccinations.
- For the 3 panels referring to aggregated data, a first run will be done without considering the intervention group. When unblind is managed, THL will generate a second run, in order to obtain dataset taking into account injected group information, i.e. aggregation by treatment group.

6 References List

- 1 Newcombe R.G., Two-sided confidence intervals for the single proportion: comparison of seven methods, *Statistics in Medicine*, (1998) 17, 857-872

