3.2 Study Plan

Randomization and Vaccination

All eligible subjects were randomized to receive a single IM injection of either QIV-HD or QIV-SD at Day 0. A scratchable list was used to randomly assign subjects to either the QIV-HD group or the QIV-SD group. All subjects were observed for 20 minutes after vaccination to ensure their safety.

Recording of Data

Finland uses multiple registers to collect different health and population data. Subject data were recorded in the local medical patient file by health care professionals (HCPs). From patient files the data was transferred automatically to the corresponding Finnish health registers (hospital diagnosis/treatment and SAEs).

Collection of Datasets

The datasets were collected using multiple Finnish health registers and compiled by THL into an analysis database. The subject's Personal Identity Code (PIC) constituted the common key between all of the registers. On a regular basis, THL extracted the study data from the different Finnish registers and when required from local medical patient files. THL submitted protocol-defined datasets to Sanofi Pasteur in a pseudonymised manner (ie, PIC will not be transferred to Sanofi Pasteur to maintain data privacy).

Collection of safety data

Serious adverse reactions (SARs) and AESIs, experienced by the subject and suspected to be related to the vaccine according to the HCP assessment, were collected using an SAR/AESI paper form throughout the study (ie, from inclusion up to 31 August of the year following the vaccination). All fatal SAEs, irrespective of causality, were collected for the same period using real-time surveillance of population data. Additional data could be collected from the local medical patient file, as needed.

All SAEs resulting in hospitalization were collected by THL from the Finnish health registers up to 6 months after vaccination. AESIs, which had not been reported by the HCPs, were collected from the Finnish health registers up to 6 months after vaccination, and reported as eSAE.

Note: AESIs included new onset of Guillain-Barré syndrome (GBS), encephalitis / myelitis (including transverse myelitis), Bell's palsy, optic neuritis, and brachial neuritis.

4 Endpoints and Assessment Methods

See Section 9 of the protocol.

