4.2 Secondary Endpoints and Assessment Methods

4.2.1 Effectiveness

See Section 9.2.1 of the protocol.

As described in [Section 5.7](#) of the SAP Core Body:

- the following I16, I75 and I76 codes were not included in the secondary objectives
- the MACE was not produced, but an analysis linked to MACE ICD-10 codes
- the flu peak period was not conducted as statistical analysis
- The panels from KELA were based on aggregated data

Based on HILMO data, no status on death was available. Death is reported through the eSAE panel. No formal cross analysis between HILMO and eSAE was conducted.

When analysis is based on "primary and secondary", the number of occurrences refers to the number of events with at least one diagnostic (either primary or secondary) compatible with the outcome definition.

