5.1.2.2 Statistical Methods

The estimated rVE with 2-sided 95% CI will be computed in the same way as the primary objective. No hypotheses will be tested, but depending on the number of the first occurrence observed, the lower bound of the 2-sided 95% CI may be used for results interpretation.

The rVE with 95% CI will be computed only if at least 5 occurrences in total of the both groups and at least 1 for QIV-SD group are present.

Several analyses will be displayed per factor such as season, delay since vaccination, site localization, age (in class or continuous variable), sex, or specific comorbidities. An analysis will be also done excluding cases potentially linked to a COVID-19 occurrence.

In addition, a complementary analysis available in the appendix 15 of the Clinical Study Report (CSR) will be conducted based on person-year as denominator.

KM curves will be also produced for some endpoints. The occurrences are based on first occurrence corresponding to the endpoint analyzed. The data collection period will vary depending on the injection date, and censored in case of first occurrence of the endpoint or date of death or voluntary withdrawal (expected to be rare). See also 4.3.3.3.

The safety endpoints, per subject, will be summarized per vaccine group, with 95% CI for the main endpoints. CIs will be calculated using Clopper-Pearson method.

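### Can relative effectiveness by comorbidity still be estimated when the comorbidity panel reaches the sponsor only as aggregated data?

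*SAP*

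**What the plan says.** Secondary objective 4 (SAP 2.2) still covers groups with specific comorbidities. SAP 5.1.2.2 lists the display factors, among them "age (in class or continuous variable), sex, or specific comorbidities", and computes secondary rVE in the same way as for the primary endpoint. It adds a reporting rule: "The rVE with 95% CI will be computed only if at least 5 occurrences in total of the both groups", with at least one of them in the QIV-SD group. Protocol 9.2.1, item 4, names the groups as diabetes, cardiovascular history and chronic lung disease.

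The panel list in SAP section 4 contains one comorbidity source: "Thl_chro, corresponding to aggregated data for chronic diseases (comorbidity"), taken from KELA reimbursement data. SAP 5.7 gives the reason for aggregation: "it was decided to obtain only aggregated data for 3 panels due to complex data privacy processes". SAP 4.2.1 repeats the point under secondary effectiveness: "The panels from KELA were based on aggregated data".

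SAP 5.7 then describes two runs of these three panels. The first ignores vaccine group. For the second, after unblinding, "THL will generate a second run, in order to obtain dataset taking into account injected group information, i.e. aggregation by treatment group".

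Two other statements matter. On data structure, SAP section 4 says: "A Data Transfer Agreement (DTA) document is available as version 4.0, and describes all data available for the study". On linkage, SAP 3.2 says that the personal identity code "constituted the common key between all of the registers".

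**The concern.** An rVE within a comorbidity group needs four counts: first-occurrence cases and subjects in each arm. If the aggregated panel is split by vaccine group and nothing else, the sponsor receives the subjects but not the cases. Neither the rVE nor the SAP's own reporting rule could then be evaluated by comorbidity. Separate totals for overlapping conditions would not give a combined group either. That matters for cardiovascular history, since Protocol 5.2.6 lists three separate cardiac conditions.

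The silence stands out because SAP 4.2.1 and 5.7 deal openly with other data limits: the MACE analysis is adapted, the flu peak analysis is dropped and three ICD-10 codes are removed. At stake is the comorbidity half of a declared secondary objective. It could end without an estimate, or with a table laid out after unblinding, and SAP section 5 calls such later work post-hoc and exploratory.

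**Working it through.** **Inputs.** About 450 cases in the only season, 2200 planned cases, design rVE 13%, 1:1 allocation and one-sided alpha 0.025 (all SAP 5.5). The rVE formula and exact interval come from SAP 5.1.1. The share of cases arising in a comorbidity group is not given; 20%, 30% and 50% are assumed below.

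**Step 1: the plan's own figure.** Given the total number of cases n, the QIV-HD count is binomial with q = (1 − rVE)/(2 − rVE) = 0.87/1.87 = 0.4652. Superiority requires the upper Clopper-Pearson limit for q to lie below 0.5. With n = 2200 that means at most 1053 QIV-HD cases, and the probability of this is 0.8999. The stated 90.0% reproduces.

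**Step 2: would subjects per arm alone be enough?** No. Assume equal arms, 209 QIV-HD and 241 QIV-SD cases overall (rVE = 1 − 209/241 = 13.3%), and a comorbidity group of equal size in each arm that supplies 135 cases (30% of 450). Two splits fit these same totals:

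| Cases in group, HD / SD | rVE | 95% CI |
|---|---|---|
| 63 / 72 | 12.5% | −24.4 to 38.6 |
| 72 / 63 | −14.3% | −62.9 to 19.6 |

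So the algebra behind the concern is right: without case counts by comorbidity, the estimate is not identified.

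**Step 3: does the SAP say that only subjects per arm will be delivered?** Set the two runs in SAP 5.7 side by side. The first is without vaccine group; the second is the same output with vaccine group added. The sentence records that difference. It covers comorbidity, care allowance and medication together, yet it names no condition, allowance status, drug class or follow-up period. Each panel needs some of these as a dimension: SAP 4.3.3.2 has five comorbidity factors, and Protocol 2.3 requires three follow-up periods for functionality and health care use. If a dimension not named there were taken as absent, none of the three panels could serve its purpose, and even the number of subjects per condition would be missing. The sentence cannot be the full layout.

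**Step 4: does the SAP treat the analysis as lost?** No. SAP 5.7 says that aggregation stops individual data for the affected secondary and observational endpoints from going to authorities. Care allowance and medication are observational (Protocol 9.3, items 2 and 3). The secondary endpoint that draws on a KELA panel is the comorbidity grouping (Protocol 9.2.1, item 4). The SAP therefore keeps that endpoint and states one consequence for it, which concerns data submission.

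**Step 5: what precision is in play?** At an assumed true rVE of 13%, with case splits giving 12.5%:

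| Share of 450 cases | Cases (HD / SD) | 95% CI for rVE 12.5% | Power at true rVE 13% |
|---|---|---|---|
| 20% | 90 (42 / 48) | −35.2 to 43.6 | 8.9% |
| 30% | 135 (63 / 72) | −24.4 to 38.6 | 10.3% |
| 50% | 225 (105 / 120) | −14.7 to 33.3 | 16.9% |
| all | 450 (209 / 241) | −4.8 to 28.3 (rVE 13.3%) | 29.0% |

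These widths apply with the case counts fully supplied. They describe how little the analysis can show in one season. They do not measure any harm from an unwritten layout.

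**The case for a change.** The strongest case for a change is that a plan approved before unblinding ought to show how each retained analysis will be produced. Nothing in the SAP mentions a split by case status. The reporting rule is easily met for the primary endpoint: 5 of 450 cases is 1.1%, so a comorbidity rVE would normally be reported. The remedy also looks cheap. For the primary endpoint, four counts times seven groupings (five factors, combined cardiovascular history, any comorbidity) make 28 numbers, with no individual KELA record leaving THL.

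Part of this stands. The SAP does not state the cross-tabulation, and a pointer to the relevant table of the Data Transfer Agreement would have spared the reader the question.

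The rest is weaker. The comorbidity groups, endpoints, formula and reporting rule are already fixed, so asking THL for cases and subjects per arm in those groups leaves little room for choice after unblinding. The first run, without vaccine group, evidently precedes unblinding, so a missing dimension would show while the data are still blinded. THL works from linked records and can form combined groups before export; nothing says that only separate totals are delivered. Nor is the remedy as small as 28 numbers. Protocol 9.2.1, item 4, covers each listed endpoint, and its nine hospitalization categories alone add 2 × 7 × 9 = 126 case counts. That detail belongs in a data transfer specification more than in SAP 5.7.

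**Conclusion.** No change is called for. This is a gap in description that the analysts fill in the ordinary course of the work: nobody can compute rVE by comorbidity without asking for cases as well as subjects, and THL holds the linked data to supply both. No stated rule gives a wrong result, and the documents do not show that the analysis cannot be produced.

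The consequence is small in any event. The analysis is descriptive and untested (SAP 5.1.2.1), in a study stopped after one season and declared inadequately powered even for its primary endpoint (SAP 5.7). Power by comorbidity is about 9% to 17% at an assumed 20% to 50% share of cases, and the primary analysis does not use the KELA panels.

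The conclusion rests on two things that the documents do not settle. The Data Transfer Agreement was not available, so its layout is unknown. It is also assumed that THL can tabulate linked KELA and hospital data by case status within the privacy terms agreed. If that were refused, the comorbidity rVE would have to be reported as not performed, again with no effect on the primary result.
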